9.1.3 Physical Examination Procedure

A physical examination will consist of the following body systems: (1) eyes; (2) ears, nose, throat; (3) cardiovascular system; (4) respiratory system; (5) gastrointestinal system; (6) dermatologic system; (7) extremities; (8) musculoskeletal system; (9) nervous system; (10) lymph nodes; (11) other. All subsequent physical examinations should assess clinically significant changes from the assessment performed before the study drug administration.

9.1.4 Weight, Height, and BMI

A subject should have weight and height measured while wearing indoor clothing and with shoes off. The BMI is calculated using metric units with the formula provided below: The Takeda standard for collecting height is centimeters without decimal places and for weight it is kilograms (kg) with 1 decimal place. BMI should be derived as:

Metric: $BMI = \text{weight (kg)}/\text{height (m)}^2$

Height in centimeters (cm) will be rounded to integers and weight in kilograms (kg) will be rounded to 1 decimal place. BMI will be rounded to 1 decimal place.

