5.2 Endpoints

5.2.1 Primary Endpoints

Safety:

AEs, anthropometric (weight, height, and body mass index [BMI]) measurements, laboratory tests, resting 12-lead electrocardiogram (ECG), and vital signs (office standing blood pressure, office sitting pulse rate, office standing pulse rate, and home sitting blood pressure)

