7.1 Inclusion Criteria

Subject eligibility is determined according to the following criteria prior to entry into the study:

1. In the opinion of the investigator or subinvestigator, the subject's parent or the subject's legal guardian is capable of understanding and complying with protocol requirements.
2. The subject's parent or the subject's legal guardian is capable of signing and dating a written, informed consent form on behalf of the subject prior to the initiation of any study procedures. Written informed assent is also obtained from the subject as much as possible.
3. The Japanese subject who has a diagnosis of hypertension. A subject is eligible if he/she is deemed hypertensive according to the reference blood pressure values of children by gender and age (Table 5.a); office sitting diastolic or systolic blood pressure ≥ 95 percentile for essential hypertension without concomitant hypertensive organ damage, and ≥ 90 percentile for secondary hypertension with concomitant CKD, diabetes mellitus, heart failure or any hypertensive organ damage.

In addition, subjects need to meet the following criteria:

- (1) If currently treated with any antihypertensive drugs at the start of the Run-in Period: Subject has a documented historical diagnosis of hypertension and an office sitting diastolic or systolic blood pressure meeting the above criteria at the end of the Run-in Period (Week 0).
- (2) If currently untreated with any antihypertensive drugs at the start of the Run-in Period: Subject who meets the above criteria on 3 separate time points including screening and the end of the Run-in Period (Week 0). In addition, subject with essential hypertension without concomitant hypertensive organ damage still maintains hypertension with non-pharmacotherapy including foods or exercises for at least 3 months within 1 year prior to the start of screening.
4. The subject is male or female and aged 6 to less than 16 years at the time of informed consent.
5. The subject weighs at least 20 kg at screening.
6. The subject is capable of taking the tablets or granules supplied as the study drug.

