13.1.5 Safety Analysis

[Primary endpoints]

AEs, anthropometric (weight, height and BMI) measurements, laboratory tests, resting 12-lead ECG, and vital signs (office standing blood pressure, office sitting pulse rate, office standing pulse rate, and home sitting blood pressure)

[Analytical methods]

The following analyses will be conducted with the safety analysis set.

1) AEs (Treatment-emergent AEs)

A treatment-emergent AE (TEAE) is defined as any AE occurring after the start of TAK-536 administration of the Treatment Period.

The incidence of TEAEs listed below will be analyzed. TEAEs will be coded using the Medical Dictionary for Regulatory Activities (MedDRA). The frequency distribution will be provided using the system organ class (SOC) and preferred term (PT) using MedDRA as follows:

- TEAEs
 - Drug-related TEAEs
 - Severity of TEAEs
 - Severity of drug-related TEAEs
 - TEAEs leading to study drug discontinuation
 - Serious TEAEs
 - TEAEs over time
- 2) Anthropometric (weight, height and BMI) measurements, laboratory tests, resting 12-lead ECG, and vital signs (office standing blood pressure, office sitting pulse rate, office standing pulse rate, and home sitting blood pressure)

For continuous variables, the observed values and the changes from the end of the Run-in Period (Week 0) will be summarized for each time point. In addition, individual figures of the observed values will be provided.

For categorical values, shift tables of the data before and after administration will be provided.

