Visit	Scheduled Study Day	Acceptable Time Window		
V 151t	Scheduled Study Day	Study Day	Follow-up Day	
At the End of Run-in Period (Week 0)	Study Day: 1	-28 to 1		
Week 12	Study Day: 85	2 to 127	< 4	
Week 24	Study Day: 169	128 to 267	< 4	
Week 52	Study Day: 365	268 to 379	< 4	

Table 7.d Visit Window of Height and Weight

Visit	Scheduled Study Day	Acceptable Time Window		
V 151t	Scheduled Study Day	Study Day	Follow-up Day	
At the End of Run-in Period (Week 0)	Study Day: 1	-28 to 1		
Week 12	Study Day: 85	2 to 127	< 15	
Week 24	Study Day: 169	128 to 225	< 15	
Week 40	Study Day: 281	226 to 323	< 15	
Week 52	Study Day: 365	324 to 379	< 15	

Table 7.e Visit Window of Resting 12-lead ECG

Visit	Scheduled Study Day	Acceptable Time Window	
V ISIL	Scheduled Study Day	Study Day	Follow-up Day
At the End of Run-in Period (Week 0)	Study Day: 1	-42 to 1	
Week 12	Study Day: 85	2 to 127	< 15
Week 24	Study Day: 169	128 to 267	< 15
Week 52	Study Day: 365	268 to 379	< 15

Table 7.f Visit Window of Plasma Drug Concentration (day of blood sample collection)

Visit	Scheduled Study Day	Acceptable Time Window
v isit	Scheduled Study Day	Study Day
Week 2 (predose, postdose)	Study Day: 15	2 to 22
Week 4 (predose, postdose)	Study Day: 29	23 to 43
Week 8 (predose, postdose)	Study Day: 57	44 to 71
Week 12 (predose, postdose)	Study Day: 85	72 to 99
Week 16 (postdose)	Study Day: 113	100 to 127

Table 7.g Visit Window of Plasma Drug Concentration (time of blood sample collection)

Time Point	-	ne Interval between the Latest Study Drug Administration and the Blood Sample Collection	
	Scheduled Time	Acceptable Time Window	
Predose	24 hours	21 to 27 hours	
Postdose	2 hours	1 to 3 hours	

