7.11.3 Vital Signs and Weight

Analysis set:

Safety analysis set

Analysis variable(s):

Office sitting pulse rate

Office standing systolic blood pressure, Office standing diastolic blood pressure, Office standing pulse rate

Home sitting systolic and diastolic blood pressures

Height, Weight

Visit

Office sitting pulse rate: Weeks 0, 2, 4, 8, 12, 16 (postdose), 20, 24, 32, 40, 52, 54 (Follow-up Period)

Office standing blood pressure and pulse rate: Weeks 0, 12, 24, and 52

Home blood pressure: Week 0 (predose), Week 0 (postdose), Weeks 2, 4, 8, and 12

Height and weight: Weeks 0, 12, 24, 40, and 52

Analytical method(s):

The following analysis will be performed for the above analysis variables by weight group (\leq 50 kg, \geq 50 kg) and in the combined weight groups.

The measurement of office sitting pulse rate at Week 16 will be performed after the study drug administration, while the measurement at other visits than Week 16 will be performed before the study drug administration.

(1) Summary statistics for observed values and changes (each visit after administration [each visit other than Week 0] – Week 0) will be provided for each visit.

Home blood pressure will be provided for changes (each visit after administration [each visit other than Week 0 (predose)] – Week 0 [predose]).

- (2) Case Plots
- (3) Overall frequency distributions of home blood pressure during the Treatment Period. See "9.0 APPENDIX" for the criteria."

7.11.4 **12-Lead ECGs**

Analysis set:

Safety analysis set

Analysis variable(s):

Heart rate

RR interval

PR interval

QT interval

QTcF interval

QRS interval

Resting 12-lead ECG interpretation [Within normal limits, Abnormal but not clinically significant, Abnormal and clinically significant]

Visit:

Weeks 0, 12, 24, and 52

Analytical method(s):

The following analyses (1) and (2) will be performed for the above analysis variables excluding resting 12-lead ECG interpretation by weight group ($< 50 \text{ kg}, \ge 50 \text{ kg}$) and in the combined weight groups.

The following analysis (3) will be performed for resting 12-lead ECG interpretation by weight group ($< 50 \text{ kg}, \ge 50 \text{ kg}$) and in the combined weight groups.

- (1) Summary statistics for observed values and changes (each visit after administration [Week 12 to Week 52] Week 0) will be provided for each visit.
- (2) Case Plots
- (3) Shift tables at Week 0 and each visit after administration

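### Height, part of the primary safety endpoint in growing children, is recorded in whole centimetres; this adds avoidable noise to individual and short-interval height changes, though hardly to the group means

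*Protocol*

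**What the plan says.** Protocol 5.2.1 makes height part of the primary endpoint: "AEs, anthropometric (weight, height, and body mass index [BMI]) measurements, laboratory tests, resting 12-lead electrocardiogram (ECG), and vital signs". Inclusion criterion 4 in Protocol 7.1 sets the age range: "The subject is male or female and aged 6 to less than 16 years at the time of informed consent".

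Protocol 9.1.4 fixes the recording precision. It gives the origin of the rule, "The Takeda standard for collecting height is centimeters without decimal places", and then states it: "Height in centimeters (cm) will be rounded to integers and weight in kilograms (kg) will be rounded to 1 decimal place". No reason specific to this trial is given. Weight and BMI each keep one decimal.

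SAP 7.11.3 lists the visits: "Height and weight: Weeks 0, 12, 24, 40, and 52". The planned outputs are summary statistics of observed values and of change from Week 0 at each visit, by weight group and combined, plus case plots. Protocol 13.1.5 likewise promises that "individual figures of the observed values will be provided". Neither document plans a visit-to-visit change, a growth velocity or a rule that classifies a child as not growing. Neither gives a growth rate, a between-child SD or a measurement error for height.

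**The concern.** The intervals between height visits are 12, 12, 16 and 12 weeks. Over 12 weeks the expected gain of a school-age child is of the same order as the recording unit, so a recorded change can take only a few values (0, 1, 2 or 3 cm). The Week 12 and Week 24 changes and the case plots are where slowed growth would first be visible, and they are also where a 1 cm grid matters most. Rounding at data entry is irreversible: a visit on an odd day can be allowed for later because its date is known, but a discarded decimal cannot be restored. Derived quantities inherit the error. BMI is reported to 0.1 kg/m², and the eGFR formula in Protocol 9.1.9 uses the most recent height.

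**Working it through.** **The plan's own figure.** There is none for height. The only design figure is the blood pressure power in Protocol 13.3. Recomputed with the noncentral t (n = 50, two-sided 0.05), it is 99.0% for diastolic and 98.9% for systolic, consistent with the stated 90% or more. It has no bearing on height.

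**Inputs.** From the documents: recording unit 1 cm (Protocol 9.1.4); visits at Weeks 0, 12, 24, 40 and 52 (SAP 7.11.3); 50 subjects (Protocol 13.3). Assumed, because the documents are silent: growth of 2 to 5.6 cm/year; velocity SD 1 cm/year (0.23 cm over 12 weeks), or alternatively a between-child SD of 0.5 to 0.7 cm in 12-week growth; measurement SD 0.3 cm per reading.

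**1. Rounding noise.** For a recording unit u, the SD per reading is u/√12 and the SD per change is √2·u/√12.
- u = 1 cm: 0.289 cm per reading, √(2/12) = 0.408 cm per change.
- u = 0.1 cm: 0.041 cm per change.

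At 5 cm/year the 12-week gain is 5 × 84/365.25 = 1.15 cm, so 0.41 cm is about 35% of it. The 52-week gain is 4.98 cm, and 0.41 cm is about 8% of that.

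**2. Rounding with no other source of error.** With true growth g and the fractional part of baseline height uniform, P(recorded change = 0) = max(0, 1 − g). A zero therefore needs true growth under 1 cm. Over 12 weeks that is a velocity below 365.25/84 = 4.35 cm/year; for change from Week 0 the threshold falls to 2.17 at Week 24, 1.30 at Week 40 and 1.00 at Week 52. At 12 weeks the probability is 54% at 2 cm/year, 31% at 3, 8% at 4, and 0% at 5 or more.

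**3. SD of the Week 12 change.** With between-child SD s and measurement SD m, SD = √(s² + 2m² + u²/6), where 2m² = 0.18.

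| s (cm per 12 weeks) | 0.1 cm recording | 1 cm recording | Increase |
|---|---|---|---|
| 0.23 | √(0.053 + 0.18 + 0.002) = 0.48 | √(0.053 + 0.18 + 0.167) = 0.63 | 30% |
| 0.5 | √(0.25 + 0.18 + 0.002) = 0.66 | √(0.25 + 0.18 + 0.167) = 0.77 | 18% |
| 0.7 | √(0.49 + 0.18 + 0.002) = 0.82 | √(0.49 + 0.18 + 0.167) = 0.91 | 12% |

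**4. Share of recorded 12-week changes at or below zero** (simulation; measurement SD 0.3 cm, velocity SD 1 cm/year).

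| Velocity (cm/year) | 0.1 cm | 1 cm |
|---|---|---|
| 5.6 | 0.5% | 8% |
| 5 | 1% | 13% |
| 4 | 4% | 23% |
| 3 | 9% | 37% |
| 2 | 20% | 53% |

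With growth of 1.3 cm in 12 weeks and the wider between-child SDs, the shares are 3% against 13% (s = 0.5) and 6% against 18% (s = 0.7).

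**5. Group mean.** In simulation the mean recorded change equals the mean true change (1.15 and 1.15 cm at 5 cm/year). The standard error of the Week 12 mean at N = 50 rises by (0.63 − 0.48)/√50 = 0.02 cm when s = 0.23, and by (0.77 − 0.66)/√50 = 0.016 cm when s = 0.5.

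**6. Week 52.** The same formula gives an SD increase of about 7% for a between-child SD of 1 cm in 52-week growth (1.08 to 1.16), and 2 to 3% for 1.5 to 2.0 cm.

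**7. Derived quantities.** A worst-case 0.5 cm error at 115 cm and BMI 16 shifts BMI by 2 × 0.5/115 × 16 = 0.14 kg/m², about 0.9%. In the Protocol 9.1.9 formulas the same error moves the height-based reference creatinine by under 0.8%, and eGFR by slightly less because of its added constant.

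**The case against.** The strongest reply is that no planned conclusion depends on this. The study has a single arm, with no test and no decision rule on height. The summaries are means of change from Week 0, which rounding does not bias and barely widens. Rounding error does not accumulate while slowed growth does, so five readings over 52 weeks would still separate the two in most children. The SAP's own Week 12 height window (Table 7.d in section 7.1.3, Day 2 to 127) admits 125 × 5/365.25 = 1.7 cm of true growth at 5 cm/year, more than rounding adds. All of this stands, and it limits the point to individual and early readings. It does not justify discarding the decimal: visit timing can be allowed for afterwards, rounding cannot.

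A reader might go further and infer that rounding alone makes many normally growing children look as if they had stopped growing. The documents do not support that. They give no growth rate, and step 2 shows that at an assumed 5 cm/year or more rounding alone produces no zero readings. The shares in step 4 need measurement error and between-child variation as well. In the scenarios with 1.3 cm of growth in 12 weeks, only 3.3% (s = 0.5) or 2.4% (s = 0.7) of children truly grow at least 1 cm yet read zero or less. The share of zeros is also this review's yardstick, not an output that the SAP plans.

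**Conclusion.** The point holds as a modest matter of precision. Whole-centimetre recording adds an SD of 0.41 cm to every height change where 0.1 cm recording would add about 0.04 cm. Under the stated assumptions it widens the SD of the Week 12 change by roughly 12 to 30%, the larger figure applying when children differ little in growth. It makes zero or negative 12-week readings clearly more frequent, most of all in slow growers: at 3 cm/year over a third would read as no growth, against 9% at the finer precision. How many such children will be enrolled is not stated.

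The point does not extend to the group results. The mean change is unbiased, its standard error at Week 12 grows by about 0.02 cm, and the effect at Week 52 is small. The effects on BMI and eGFR are about 1% or less. The rounding SDs follow from the recording unit alone; every percentage rests on growth and measurement values from outside the documents, which is why ranges are shown.

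**What to change.** In Protocol 9.1.4 and in the eCRF field format, record height to 0.1 cm. Derive BMI, and the height term in the eGFR formula of 9.1.9, from that recorded value, and round only for display in tables and listings. The SAP's analyses of height need no change.

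The cost is one protocol sentence and one eCRF field format, with no added visit, procedure or staff time. The downside is a departure from the company's collection standard. Heights already entered in whole centimetres can be refined only if the source records hold the decimal.

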9.1.5 Vital Sign Procedure

Vital signs will include office sitting blood pressure (systolic and diastolic), office standing blood pressure (systolic and diastolic), office sitting pulse rate, and office standing pulse rate (pulse rate per 1 minute). All office blood pressure will be measured with a blood pressure meter specified by the sponsor.

Office blood pressure should be measured at the time of trough (approximately 21 to 27 hours after the latest dose, i.e., in the morning of that day) with the subject without taking the study drug in the morning of the scheduled visit except for Week 16. The subject, the subject's parent, or legal guardian will be instructed strongly not to take the study drug at home on the scheduled visit day except for Week 16. The subject, the subject's parent, or the subject's legal guardian will be instructed again if the subject receives the study drug before the measurements of vital signs on the scheduled visit day by mistake.

When vital signs are scheduled at the same time as blood draws, vital signs will be obtained before the scheduled blood draw.

Office sitting blood pressure after taking the study drug will be also measured only at Week 16 of the Treatment Period; the time point which the pharmacokinetics after receiving the study drug is evaluated.

Subjects will be instructed not to eat or bathe within 1 hour before office blood pressure measurement, not to intake any caffeine containing product 30 minutes before the measurement.

<Determining difference in blood pressure between right and left arm>

At screening, sitting blood pressure in the right and left arms will be measured once after sitting at rest for ≥ 5 minutes to determine the difference in blood pressure between the arms. The arm with a higher systolic blood pressure will be used to measure office blood pressure during the study.

The right arm will be used if systolic blood pressure is the same on both sides. Change of the arm for measurement will not be allowed during the study.

<Measuring sitting blood pressure and sitting pulse rate>

Sitting blood pressure will be repeatedly measured 3 times at 1 to 2 minute intervals after the subject has been sitting at rest for at least 5 minutes and recorded in the subject source documents and eCRF. However, if 2 of the 3 systolic blood pressure measurements differ by more than 8 mmHg or diastolic blood pressure measurements differ by more than 5 mmHg, a second set of 3 sitting blood pressure measurements should be obtained and only the second set of readings should be recorded in the eCRF (even if these still differ by > 8 mmHg for systolic blood pressure or 5 mmHg for diastolic blood pressure). Original and repeat readings must all be recorded in the source documents with an explanation.

The arithmetic mean (rounded to integers) of 3 measurements of a session will be used for determination of the subject eligibility.

The pulse rate measured at the last measurement of the sitting blood pressure will be used as the sitting pulse rate value.

Sitting blood pressure must be measured after resting in a sitting position for at least 5 minutes. An appropriately sized cuff (40% of the arm's perimeter) should be used, and applied to an upper arm held at the heart level. All measurements must be made on the same arm using the same-sized cuff. Every effort should be made to standardize the condition of office blood pressure measurements as possible, such as measurement time, the same blood pressure device should be used, whenever possible, by the same investigator, subinvestigator, or the study collaborator.

<Measuring standing blood pressure and standing pulse rate>

Standing blood pressure will be measured to evaluate the orthostatic vital signs at the scheduled visit of Week 0, 12, 24 and 52. After measuring the sitting blood pressure, standing blood pressure will be measured once after the subject has been standing for 2 minutes. Standing systolic and diastolic blood pressure will be also measured with the same device which measures sitting blood pressure on the same arm. For standing blood pressure measurements, the arm should be supported and extended such that the cuff is at heart level. Standing pulse rate will be measured once during the subject maintains a standing position.

9.1.6 Measuring Home Blood Pressure

Each subject, the subject's parent, or the subject's legal guardian will be provided a home blood pressure meter and adequately informed of the measurement procedures at the start of the Run-in Period (Week -2) by the sponsor through the study site.

The subject, the subject's parent, or the subject's legal guardian will be instructed to measure home blood pressure (systolic and diastolic), preferably consecutive 2 times daily immediately before the study drug administration for 1 week each before and after the visit at the start of the Treatment Period I, and for 1 week after the following day of a visit of each time point between Week 2 and Week 8 of the Treatment Period I (including visit at Week 6, when performed), and for 1 week from the day before the visit at Week 12 of the Treatment Period I.

The subject should measure blood pressure 2 times in a row after having been sitting for at least 5 minutes with the blood pressure cuff applied to the same arm as used to measure blood pressure at the visits. The blood pressure measurements should be recorded in patient diary and reviewed by the investigator or subinvestigator at each visit. The blood pressure measured twice immediately before the study drug administration should be recorded in CRFs. The subject, the subject's parent, or the subject's legal guardian will be instructed to inform the study site if a home sitting systolic blood pressure which is higher by at least 15 mmHg and/or a home sitting diastolic blood pressure which is higher by at least 10 mmHg than the 99 percentiles of the reference blood pressure values of children by gender and age in Table 5.a. The subject, the subject's parent, or the subject's legal guardian will be instructed by the investigators to visit the study site to measure blood pressure again if needed. If the elevated blood pressure is confirmed by repeat measurements at the study site, the subject is to be considered to discontinue the study.

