When the antihypertensive drugs are required dose reduction or interruption because of the concerns in tolerability with titration (i.e., excessive reduction in blood pressure, other AE, etc.) in the Treatment Period II, the antihypertensive drugs other than TAK-536 (in case of concomitant use) should be reduced or interrupted first. Thereafter, dose reduction or interruption of TAK-536 should be considered.

[figure not shown]
(4) Follow-up Period

Follow-up Period will be 2 weeks from the next day of the final dose of TAK-536. Safety will be evaluated at Week 54 after the start of the Treatment Period.

At the time when the data from approximately 25 subjects are collected, the data until Week 12 in the Treatment Period will be analyzed. In addition, at the time when all subjects complete Week 24 in the Treatment Period, the data until Week 24 in the Treatment Period will be analyzed separately after being locked. These analyses will not intend to continue or discontinue this study.

A schematic of the study design is included as Figure 6.a. A schedule of assessments is listed in Appendix A.

Figure 6.a Schematic of Study Design

- 1) The subjects whose blood pressures meet the inclusion criteria 1 (at earliest) week after receiving placebo in the Run-in Period can enter the Treatment Period. For the subjects only who treated with any antihypertensive drugs as a prior treatment only, the Run-in Period could be extended up to 4 weeks if blood pressures do not meet the inclusion criteria.
 - 2) If subjects have difficulty in discontinuing antihypertensive drugs completely at the start of the Run-in Period, the antihypertensive drugs can be down-titrated concurrently with administration of placebo. In the case of the down-titration, antihypertensive drugs should be discontinued at least 1 week (7 days) before the start of the Treatment Period I. Especially, beta-blockers (BBs) should be tapered off gradually since sudden discontinuation of BBs may cause withdrawal syndrome.
 - 3) In the Treatment Period I, TAK-536 can be titrated biweekly when the subjects do not achieve the target blood pressure while evaluation of safety and tolerability. TAK-536 can be reduced at the investigator's or subinvestigator's discretion if there are any concerns in tolerability with titration of TAK-536 (i.e., in case of occurring any AEs caused by titration of TAK-536).

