For home blood pressure, the mean of 2 values on a given measuring day will be used as the representative value of that measuring day (do not round off). If only one measurement is performed on a given measuring day, that value will be used as the representative value. Next, based on Table 7.h, the mean of the representative values on each measuring day within each acceptable time window (rounded to integers) will be used as the values for each visit. However, if the representative values on the measuring day within the time window include values for 3 days or less, this visit will be handled as missing. At the End of Treatment Period I, among the values from Week 0 (postdose) to Week 12 included based on Table 7.h, the value at the last visit excluding missing data will be used. If the acceptable time window overlaps at different visits, the value will be included in the earlier visit and excluded from the later visit.

Table 7.h Visit Window of Home Blood Pressure

		Acceptable Tim	Acceptable Time Window	
Visit	Reference Day	Number of Days from Reference Day*	Follow-up Day	
Week 0 (predose)	Visit day for Week 0	−7 to −1		
Week 0 (postdose)	Visit day for Week 0	2 to 8	< 4	
Week 2	Visit day for Week 2	2 to 8	< 4	
Week 4	Visit day for Week 4	2 to 8	< 4	
Week 8	Visit day for Week 8	2 to 8	< 4	
Week 12	Visit day for Week 12	−7 to −1	< 4	

^{*:} The day before the Reference Day will be defined as Day -1 and the Reference Day as Day 1.

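### The protocol's Week 12 home blood pressure week most naturally runs forward from the day before the visit, but the SAP counts only the 7 days ending there; a family that measures forward loses the Week 12 value

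*Protocol*

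**What the plan says.** Protocol 9.1.6 sets three kinds of home measurement week in one sentence, and 7.4 item 5 gives families the same schedule.

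- Around Week 0: "for 1 week each before and after the visit at the start of the Treatment Period I".
- Weeks 2 to 8: "for 1 week after the following day of a visit of each time point between Week 2 and Week 8".
- Week 12: "for 1 week from the day before the visit at Week 12 of the Treatment Period I".

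SAP 7.1.3 turns daily home readings into visit values through Table 7.h. Its day numbering has no Day 0: "The day before the Reference Day will be defined as Day -1 and the Reference Day as Day 1". The accepted days are -7 to -1 for Week 0 (predose), 2 to 8 for Week 0 (postdose) and for Weeks 2, 4 and 8, and -7 to -1 for Week 12. If the daily values "within the time window include values for 3 days or less, this visit will be handled as missing". For the End of Treatment Period I, among Week 0 (postdose) to Week 12, "the value at the last visit excluding missing data will be used".

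Home blood pressure is one of the protocol's primary safety variables (5.2.1). The SAP summarises it by visit in 7.11.3. In 7.8.3 it is also an additional efficacy endpoint, by visit and at the End of Treatment Period I, with confidence intervals and a one-sample t-test for reference. SAP 7.13 records that added role but mentions no change to the Week 12 measurement week.

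**The concern.** The text that tells families when to measure and the table that decides which readings count appear to describe different weeks, and they share only one day. The other rows of Table 7.h fit the protocol wording; Week 12 is the exception.

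The by-visit home value at Week 12 and the home value labelled End of Treatment Period I are at stake. Week 12 matters because protocol 6.2 sized Treatment Period I to give four weeks at the highest dose after titration, on the ground that the largest fall in adults was seen four weeks after titration. Titration is allowed at the Week 8 visit. If Week 12 is missing, the fallback is normally the first week after Week 8, so a child titrated at that visit contributes a value from only the first week on the new dose. Home blood pressure is also the only efficacy measure that does not decide entry: protocol 7.1 criterion 3 selects on office readings.

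**Working it through.** The plan states no figure to reproduce here. The check is a day count.

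**Inputs.** Week 12 measurement week: protocol 7.4 item 5 and 9.1.6. Accepted days, day numbering and minimum-data rule: SAP 7.1.3 and Table 7.h. Nominal visit days: SAP Table 7.a (Week 8 = Study Day 57, Week 12 = Study Day 85).

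**Rule.** Count the measured days that lie in the accepted window. A visit is evaluable if that count is at least 4, since 3 or fewer means missing.

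| Reading of the Week 12 instruction | Days measured (SAP numbering) | Days within -7 to -1 | Week 12 |
|---|---|---|---|
| Forward, 7 days | -1, 1, 2, 3, 4, 5, 6 | 1 | missing |
| Forward, counted as 8 days | -1, 1, 2, 3, 4, 5, 6, 7 | 1 | missing |
| Backward, ending the day before the visit | -7 to -1 | 7 | evaluable |
| Backward, ending on the visit day | -6 to -1, and 1 | 6 | evaluable |

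**At nominal timing.** The forward week covers Study Days 84 to 90. The SAP window is 85 - 7 = 78 to 85 - 1 = 84. Only Study Day 84 is common to both.

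**Could another rule rescue the value?** The Week 8 window is Study Days 57 + 1 = 58 to 57 + 7 = 64, which does not reach Study Day 78. The overlap rule assigns a shared day to the earlier visit, so it cannot add days to Week 12. No other measurement week is scheduled between the two.

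**Fallback.** With Week 12 missing and Week 8 present, the End of Treatment Period I home value comes from Study Days 58 to 64. That week ends 85 - 64 = 21 days before the Week 12 visit.

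**Which reading is more natural?** Three features of the protocol point forward.

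- In the same sentence, the backward week at Week 0 is called a week before the visit. Week 12 is not worded that way.
- The Weeks 2 to 8 clause also names a starting day and runs forward from it.
- Protocol 6.1 uses the same construction for a forward period: "Follow-up Period will be 2 weeks from the next day of the final dose of TAK-536".

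**Size.** If a share f of the 50 planned children were measured forward, 50 × f would lose Week 12 and 50 × (1 - f) would keep it, other losses aside. The documents give no value for f, so the possible range is 0 to 50 children.

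**The case against.** The strongest reply is that a backward week was meant. Table 7.h gives Week 12 a different window from Weeks 2 to 8, which looks deliberate. Treatment Period II starts at Week 12, yet SAP 7.8.3 stops at the End of Treatment Period I, so a week lying mostly after the visit would be an odd choice. The protocol's English is loose elsewhere in the same sentence: taken strictly, the Weeks 2 to 8 clause starts on Day 3, and the SAP reads it as Day 2. If Table 7.h settles that clause, it can settle Week 12 too. The follow-up example is also weak support, since follow-up after a last dose can only run forward.

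Much of this stands as evidence of what the drafters intended. It does not remove the problem, because families follow the instruction and not the SAP. The looseness also costs differently in the two places: Days 3 to 9 against a window of 2 to 8 still leaves 6 usable days, whereas the forward week at Week 12 leaves 1.

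It also stands that the deciding material is not visible. The diary, the site training and the Appendix A schedule are not in the supplied text, and any of them may already state the days clearly.

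A reader might infer two stronger things. The first is that Week 12 home blood pressure will be missing for the whole trial. The documents do not support that, because the loss occurs only where a family measured forward. The second is that the primary safety evaluation is compromised. That is not supported either. SAP 9.3 classifies markedly high home readings from the raw recorded values at any time after the first Treatment Period dose up to 3 days after the last dose, without Table 7.h, so forward-week readings still count. Office blood pressure, the named secondary endpoint, has its own windows.

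**Conclusion.** The concern holds in conditional form. For any child measured on the forward week, 1 of 7 days counts where at least 4 are needed. The Week 12 home value is missing, and the End of Treatment Period I home value normally comes from the week after Week 8. For any child measured on the backward week, nothing is lost.

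This rests on the forward week being the more natural reading of the protocol text, on nominal visit timing for the fallback dates, and on Week 8 itself being evaluable. The number of children affected cannot be worked out from the documents.

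The damage is confined to the Week 12 row of the home summaries in SAP 7.8.3 and 7.11.3 and the End of Treatment Period I home value in 7.8.3. It should be corrected, because an operative measurement instruction whose natural reading voids a planned value is more than a matter of style. It does not threaten the trial's main conclusions.

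**What to change.** In protocol 7.4 item 5, protocol 9.1.6 and the diary instruction, replace the Week 12 clause with *for the 7 days ending on the day before the Week 12 visit*. This matches Table 7.h, keeps the readings inside Treatment Period I, and needs no change to the SAP window.

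If diaries have already gone out with the present wording, check before database lock which days around Week 12 were recorded. Report the number of children whose Week 12 home value is missing for this reason, and how many End of Treatment Period I home values therefore come from an earlier visit.

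I would not add a rescue rule that keeps post-visit days only until treatment is changed at Week 12. Such changes are driven by blood pressure, so the window would depend on the outcome. A child whose treatment changes would keep about two days (Day -1 and perhaps Day 1), still below the SAP's minimum of four.

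The cost is one sentence in each of three places, plus a count from data already collected if diaries are in use. No extra measurements are needed.
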